# 4.2 Listings to be Included in the Clinical Study Report

# 4.2.1 Listings of subject information

- 1. Listing [LDS01a] Discontinued Subjects (Blinded Phase) ITT Population
- 2. Listing [LDM01a] Demographic Characteristics (Blinded Phase) ITT Population
- 3. Listing [LRN01a] Randomization (Blinded Phase) ITT Population
- 4. Listing [LMH01a] General Medical History ITT Population
- 5. Listing [LMH02a] Special Medical History (Breast Cancer) ITT Population
- 6. Listing [LMH02a] Menstrual History ITT Population
- 7. Listing [LCM01a] Prior Medications and Treatments (Blinded Phase) ITT Population
- 8. Listing [LCM02a] Concomitant Medications and Treatments (Blinded Phase) ITT Population
- 9. Listing [LPD01a] Protocol Deviations (Blinded Phase) ITT Population

- 10. Listing [LPD02a] Protocol Deviations Lead to Exclusion from PP Population (Blinded Phase) ITT Population
- 11. Listing [LSD01a] Study Drug Compliance (Blinded Phase) ITT Population

# 4.2.2 Listings of safety data

- 12. Listing [LAE01a] Adverse Events (Blinded Phase) Safety Population
- 13. Listing [LAE02a] Serious Adverse Events (Blinded Phase) Safety Population
- 14. Listing [LAE03a] Severe Adverse Events (Blinded Phase) Safety Population
- 15. Listing [LAE04a] Study Drug Related Adverse Events (Blinded Phase) Safety Population
- 16. Listing [LAB01a] Results of Laboratory Tests Hematology (Blinded Phase) ITT Population
- 17. Listing [LAB02a] Results of Laboratory Tests Blood Chemistry (Blinded Phase) ITT Population
- 18. Listing [LAB03a] Results of Urine Pregnant Tests (Blinded Phase) ITT Population
- 19. Listing [LVS01a] Vital Signs (Blinded Phase) ITT Population
- 20. Listing [LPE01a] Abnormalities of Physical Exam (Blinded Phase) ITT Population

# 4.2.3 Listings of efficacy and PK/PD data

- 21. Listing [LEF01a] Breast Density (Blinded Phase) ITT Population
- 22. Listing [LBR01a] Breast Tissue Composition BI-RADS Grade (Blinded Phase) ITT Population
- 23. Listing [LHR01a] Hormones Results (Blinded Phase) ITT Population
- 24. Listing [LBB01a] Bone Biomarkers (Blinded Phase) ITT Population
- 25. Listing [LCR01a] Coagulation Parameters (Blinded Phase) ITT Population
- 26. Listing [LPK01a] Plasma PK Concentrations (Blinded Phase) ITT Population
- 27. Listing [LEM01a] Endometrial Results (Blinded Phase) ITT Population (only if data available)

# 5. OUTPUT PLANNED FOR THE STUDY REPORT (OPEN-LABELPHASE)

#### 5.1 **Tables to be Included in Study Report**

In the following sections, the different results are presented in the order in which it is planned to make them appear in the study report.

The table templates are available in the Appendix of the SAP. The content shown in the templates does only mean as an example. It is not based on real study data or details concerning design.

#### 5.1.1 Summary of subject information

- 25. Table [TDS01b] Subject Disposition (Open-Label Phase) All Subjects
- 26. Table [TDM01b] Summary of Demographics (Open-Label Phase) ITT Population
- 27. Table [TCM01b] Summary of Medications and Treatments Ongoing from the Blinded Phase (Open-Label Phase) ITT Population
- 28. Table [TCM02b] Summary of Concomitant Medications and Treatments (Open-Label Phase) ITT Population

# 5.1.2 Summary of safety endpoints

29. Table [TAE01b] Summary of Adverse Events (Open-Label Phase) – Safety Population

- 30. Table [TAE02b] Number (%) of Subjects with Adverse Events by Body System and Preferred Term (Open-Label Phase) Safety Population
- 31. Table [TAE03b] Number (%) of Subjects with Serious Adverse Events by Body System and Preferred Term (Open-Label Phase) Safety Population
- 32. Table [TAE04b] Number (%) of Subjects with Severe Adverse Events by Body System and Preferred Term (Open-Label Phase) Safety Population
- 33. Table [TAE05b] Number (%) of Subjects with Study Agent Related Adverse Events by Body System and Preferred Term (Open-Label Phase) Safety Population
- 34. Table [TAE06b] Number (%) of Subjects with Adverse Events by Preferred Term and Overall Frequency (Open-Label Phase) Safety Population
- 35. Table [TVS01b] Summary of Vital Signs and Change from Baseline (Open-Label Phase) Safety Population
- 36. Table [TPE01b] Summary of Physical Examination (Open-Label Phase) Safety Population
- 37. Table [TLB01b] Summary of Laboratory (Hematology) Test Results (Open-Label Phase) Safety Population
- 38. Table [TLB02b] Summary of Laboratory (Blood Chemistry) Test Results (Open-Label Phase) Safety Population
- 39. Table [TLB03b] Summary of Urine Pregnancy Test Results (Open-Label Phase) Safety Population

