#### 1.2 Design

This is a multi-center, randomized, double-blind, placebo-controlled study in women identified as having dense breast tissue upon screening mammography.

Subjects who give informed consent will have screening evaluations, including hormone measures of FSH, Estradiol and Estrone to determine menopausal state. Those subjects meeting entry criteria, will be stratified, based on their hormone levels, into pre/peri and post menopause groups and randomized within those groups 2:1 to receive either 8 mg/day (4 mg/breast) BHR-700 gel or placebo for up to 52 weeks. At the Principal Investigator's (PI) discretion, subjects may be allowed to reduce the dose to 4 mg/day (2 mg/breast) in cases of intolerance.

Subjects will apply the gel to both breasts once per day. The first dose will be applied under the supervision of the PI/designee. Subsequent doses will be self-administered daily by the subject until she has completed 52 weeks of study drug administration. Study drug compliance will be checked at each study visit. Subjects will be asked to capture daily gel administration in a diary and drug canisters will be weighed on release to the subject and on return. The canister weight will be recorded in grams. If the study drug is discontinued or interrupted, the reason(s) will be recorded. During treatment period, subjects will be evaluated at Day 1 and every 13 weeks (±2 weeks) thereafter.

A planned sample size of 330 women, identified as having dense breast tissue upon screening mammography, will be randomized to receive either BHR-700 gel or placebo (at 2:1 ratio). Considering an attrition rate of approximately 15%, it is expected to have 272 evaluable women (4-OHT: 181 & Placebo: 91) who will have both baseline and 52 week measurements of percent mammographic density (MD) of the breast.

Subjects who complete the double-blind phase of the study will be offered entry into an open-label follow-up period for an additional 52 weeks.

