# 2. ELABORATION OF STUDY PROTOCOL

#### 2.1 Study Populations

Three analysis populations will be defined and analyzed:

- 1. Intent-to-treat (ITT) population will contain all subjects who are randomized into the study. All efficacy parameters will be analyzed using the ITT population. In the case of a subject who was randomized but did not take the study drug, the analysis will be performed for this subject using the randomized treatment.
- 2. Per-protocol (PP) population will contain all ITT subjects who completed Week 52 assessments and do not have any major protocol deviation. The major protocol deviations will be identified by BH Ireland before the database is locked and unblinded.
- 3. Safety population will contain all subjects who receive at least one dose of study drug. All safety parameters will be analyzed using safety population.

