# 3.7 Key Data Items

#### Study Analysis Population Definition:

- Intended-To-Treat (ITT) population: All subjects who are randomized into the study.
- Per-Protocol (PP) population: All ITT subjects without any major protocol violations.
- Safety Population: All ITT subjects who receive at least one dose of study drug.

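### SAP Section 5 puts the open-label tables on whole-trial Safety and ITT populations; read literally, women who never entered the extension are counted in the open-label percentages

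*SAP*

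**What the plan says.** SAP 2.1 states that "Three analysis populations will be defined and analyzed". Besides the per-protocol set, these are:

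- ITT: "Intent-to-treat (ITT) population will contain all subjects who are randomized into the study".
- Safety: "Safety population will contain all subjects who receive at least one dose of study drug".

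SAP 3.7 repeats them, again without mention of phase: "Safety Population: All ITT subjects who receive at least one dose of study drug". Study drug includes placebo (Protocol 6.0), so a woman dosed once in the blinded year belongs to the Safety population.

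On entry to the extension, SAP 1.2 says: "Subjects who complete the double-blind phase of the study will be offered entry into an open-label follow-up period for an additional 52 weeks". Protocol 4.0 makes continuation the woman's choice.

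SAP Section 5 then assigns the open-label outputs. The adverse-event tables TAE01b to TAE06b, physical examination (TPE01b) and urine pregnancy tests (TLB03b) go to Safety, as in "Table [TAE02b] Number (%) of Subjects with Adverse Events by Body System and Preferred Term (Open-Label Phase) Safety Population". Demographics and the two medication tables (TDM01b, TCM01b, TCM02b) go to ITT, as in "Table [TDM01b] Summary of Demographics (Open-Label Phase) ITT Population". Disposition (TDS01b) alone is on all subjects.

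**The concern.** Each open-label table carries the name of a population fixed at randomisation or at the first dose of the trial. Women who dropped out of the blinded year, declined the extension, or were stopped by early termination are in those populations but could not have an open-label event. If they are counted in N, a percentage labelled open-label is not a rate among women exposed in the open-label phase. The demographics table on ITT would describe everyone randomised, not the women who continued.

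The stakes are in what the report is for. SAP 3.3.2 drops the efficacy analysis, and SAP 3.8 says the report will centre on safety and PK/PD, with PK/PD from the blinded phase only. The open-label output is therefore essentially safety. It is the trial's only safety information beyond Week 52, and the only information on former placebo women when they first receive BHR-700.

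**Working it through.** **The plan's own figure.** Neither document gives a denominator or an uptake for the extension, so there is no stated figure to reproduce. The two counts borrowed below are 330 planned women and 272 expected to be evaluable (SAP 1.2 and 2.3).

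**Step 1: are entrants fewer than the Safety population?** Yes. Entry requires completing the blinded phase (SAP 1.2) and is optional (Protocol 4.0). Consent and open-label supply are given at the Week 52 visit (Protocol 7.3), and SAP 3.8 records that many women had no such visit because of early termination. Writing f = entrants / Safety N, f is below 1.

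**Step 2: what a literal reading displays.** Let r be the proportion of entrants with an open-label AE, and let only events starting in the extension be counted. Then:

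displayed % = (r × entrants) / Safety N = f × r

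With entrants as the denominator, the displayed figure is r.

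**Step 3: illustrative sizes.** Take Safety N = 330 (the planned number randomised, used as a stand-in). Apart from 272/330, the values of f are pure assumptions.

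| f | Entrants | True 10% shown as | True 20% shown as |
|---|---|---|---|
| 272/330 = 0.82 | 272 | 27.2/330 = 8.2% | 54.4/330 = 16.5% |
| 0.50 | 165 | 16.5/330 = 5.0% | 33/330 = 10.0% |
| 0.25 | about 82 | 2.5% | 5.0% |

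The first row supposes that all 272 women expected to have both density measurements continue. That number is not an uptake figure.

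**Step 4: which outputs are affected.**

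- Diluted by f under the literal reading: n (%) in TAE01b to TAE06b, and the n (%) parts of TPE01b and TLB03b.
- Describing the wrong cohort: TDM01b, TCM01b and TCM02b on ITT. Age is computed at screening (SAP 3.7), so TDM01b on everyone randomised would largely repeat the blinded-phase table TDM01a.
- Not affected in this way: means of vital signs and laboratory values, which use observed data without imputation (SAP 3.8); the listings, which have no denominator; and TDS01b, on all subjects.

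**Step 5: the numerator.** SAP 3.7 calls an AE treatment-emergent if it starts on or after the day of the first study-drug dose. There is no open-label counterpart. Step 2 holds only if blinded-phase events are excluded, and no written rule excludes them.

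**The case against.** A reader might infer that the open-label AE rates will be understated and the drug made to look safer in its second year. The documents do not support that as a fact, for four reasons.

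- No sentence states what the percentages divide by. SAP 5.1 refers to table templates in an appendix, and those shells are not in the text available for this review. SAP 5.1 calls their content an example only, so they might not settle the matter, but the denominator cannot be called absent from the plan.
- The open-label tag in the titles can be read as limiting the women as well as the events, in which case nothing is diluted. Section 5 partly supports this: a table of medications carried over from the blinded phase (TCM01b) and a listing of open-label discontinuations (LDS01b) make sense only for entrants, and a separate TDM01b has a purpose only if its cohort differs from that of TDM01a.
- The downward direction requires the tag to restrict events but not women. If it restricts neither, blinded-phase events could enter the numerator and the direction is not determined.
- The size depends on f, which is not reported.

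It is also fair that the report is brief and descriptive, that no decision rule uses these percentages, and that counts are shown beside them. With open-label disposition and AE listings planned, a careful reader could probably recompute the rates.

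These arguments limit how strongly the effect can be asserted. They do not remove the defect. Sections 4 and 5 use the same population names, SAP 2.1 and 3.7 give each name one meaning, and that meaning includes women outside the extension. If the authors meant entrants, they meant a cohort that the visible text never defines, and the denominator is left to the programmer's reading.

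**Conclusion.** The concern holds as a fault in population assignment: the sets named on the open-label n (%), demographics and medication tables are whole-trial sets, and they necessarily include women who never entered the extension. Followed literally, with only open-label events counted, every open-label AE percentage is multiplied by an f below 1. A true 10% would appear as 8.2% at f = 0.82 and as 5% at f = 0.5. Both are illustrations: the first rests on planning figures that do not measure uptake, the second on an assumption. The true size cannot be computed from the documents. It is not shown that the sponsor's tables will contain this error; what is shown is that the plan as written permits it and that following the definitions produces it. The fault should be corrected before the open-label tables are run.

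**What to change.** In SAP 2.1 and 3.7, add an Open-Label Safety population: women who received at least one dose of open-label BHR-700. Then:

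- Use it as N for all tables in Section 5 except TDS01b, which can stay on all subjects.
- In SAP 3.7, count as open-label AEs those starting on or after the first open-label dose. Without this rule, correcting the denominator leaves the numerator undefined.
- Show columns for former BHR-700, former placebo and total.
- Reconcile this layout with Protocol 9.1 (Open-Label Treatment Phase) and the matching synopsis text, which plan an open-label AE comparison of BHR-700 with placebo although Protocol 7.3 supplies only BHR-700 in that phase.

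The cost is one population flag and revised table titles. No new data are needed.

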# 5.2 Listings to be Included in the Clinical Study Report

# 5.2.1 Listings of subject information

- 28. Listing [LDS01b] Discontinued Subjects (Open-Label Phase) ITT Population
- 29. Listing [LDM01b] Demographic Characteristics (Open-Label Phase) ITT Population
- 30. Listing [LCM01b] Medication and Treatments Ongoing from the Blinded Phase (Open-Label Phase) ITT Population
- 31. Listing [LCM02b] Concomitant Medications and Treatments (Open-Label Phase) ITT Population
- 32. Listing [LPD01b] Protocol Deviations (Open-Label Phase) ITT Population
- 33. Listing [LSD01b] Study Drug Compliance (Open-Label Phase) ITT Population

# 5.2.2 Listings of safety data

- 34. Listing [LAE01b] Adverse Events (Open-Label Phase) Safety Population
- 35. Listing [LAE02b] Serious Adverse Events (Open-Label Phase) Safety Population
- 36. Listing [LAE03b] Severe Adverse Events (Open-Label Phase) Safety Population
- 37. Listing [LAE04b] Study Drug Related Adverse Events (Open-Label Phase) Safety Population
- Listing [LAB01b] Results of Laboratory Tests Hematology (Open-Label Phase) ITT Population
- 39. Listing [LAB02b] Results of Laboratory Tests Blood Chemistry (Open-Label Phase) ITT Population
- 40. Listing [LAB03b] Results of Urine Pregnant Tests (Open-Label Phase) ITT Population
- 41. Listing [LVS01b] Vital Signs (Open-Label Phase) ITT Population
- 42. Listing [LPE01b] Abnormalities of Physical Exam (Open-Label Phase) ITT Population

# 7. ATTACHMENT: THE SHELLS OF TABLES, FIGURES AND LISTINGS PLANNED FOR CLINICAL STUDY REPORT

Study: BHR-700-301

Date:

